Aim 2: Conduct feasibility study in human subjects. We will conduct a randomized, non-significant risk (NSR) device study that will assess adherence and quality of life after two months use of the MT nozzle water bottle vs. control for mild-moderate OSA patients. Secondary outcome measures will compare changes in myofunctional assessment, AHI, oxygen saturation (SpO2), and snoring intensity/percentage using a clinically validated and commercially available home sleep apnea test (*WatchPAT™ One*). Myofunctional measurements will be conducted at day 0 and day 60 using an Iowa Oral Performance Instrument and a myofunctional assessment score. Water consumption will be standardized across subjects through fitting of the MT nozzle and standard nozzle on commercially available water bottles that are Bluetooth enabled to measure water consumption (*Hidrate Spark™*). A questionnaire such as SAQLI (Sleep Apnea Quality of Life Index) will be used to measure QOL. Participants' significant others will be asked to complete a bed partner survey as applicable.

Milestone: Conduct NSR device feasibility study with MT water bottle vs control that assesses adherence to therapy and quality of life after two months of use in mild to moderate OSA patients. Additionally, collect information on changes in snoring, OSA and myofunctional measures.

Our proposed nozzle is a novel, low risk, low burden, and low cost myofunctional device that will be clinically tested for feasibility with mild to moderate OSA patients. A future Phase II project would focus on further therapy optimization and conducting a larger more inclusive clinical trial with emphasis on efficacy. This proposed work has the potential to create a new therapy platform for patients to easily improve their OSA and snoring.

Inclusion Criteria:

- Diagnosis of mild to moderate obstructive sleep apnea with Apnea Hypopnea Index 5-29 events/hour confirmed within last 2 years with an in-lab diagnostic polysomnography or home sleep apnea test.
- Ownership of a smartphone and willingness to use a smartphone application to automatic log daily water intake.
- Willingness and ability to discontinue the currently prescribed OSA treatment for at least 3 days prior to testing.
- Age greater than or equal to 18 years.
- Participants willing to travel to the Rochester area for the Speech and Language Pathologist exam

Exclusion Criteria:

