Following this, the participants will conduct the home sleep apnea test using the provided WatchPAT™ ONE device for baseline measurements of pAHI (PAT Apnea Hypopnea Index), pRDI (PAT Respiratory Disturbance Index), SpO2 measures – ODI (Oxygen Desaturation Index), nadirSpO2 and T90 (Total sleep time < 90% SpO2), and snoring (intensity and percentage of night with snoring). If the subject has completed a WatchPAT clinically at Mayo Clinic within the last 3 months, the baseline WatchPAT is not required to be sent to the participant as the clinical data is accessible and will still be valid.

The measurements of the myofunctional assessment score, home sleep apnea test and questionnaires will be repeated at day 60 (\pm 5 days) after enrollment. Participants will have 15 days to complete the questionnaires after the 60 day visit.

To wash-off the remnant effects of the standard of care (SOC) OSA treatment on their upper airway, participants who are actively using CPAP, mandibular advancement device, or sleep positioning device, would be asked to discontinue the SOC treatment use for 3 nights prior to the baseline and end-of-study testing. The participants will be enrolled in the study on a rolling basis and the study coordinator will hand out randomized kits containing either MT nozzle (intervention group) or the placebo nozzle (control group), 20 participants each, as described above. The participants, PI and SLP will remain blinded to the group assignments. The study coordinator will be unblinded to group assignments. The placebo nozzle will be made out of the same silicone material and resemble the MT nozzle in appearance but will not have the resistance component to provide myofunctional exercises. The smart water bottle with Bluetooth connectivity (Hidrate Spark™) will automatically log each participant's daily fluid intake through the provided nozzle via a compatible smartphone application and share the fluid intake data with the study personnel. All participants will be suggested an intake of approximately 1.2 liters of water per day using the provided water bottle (equivalent of drinking two 20 Oz water bottles). At the

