time of study conclusion, the participants will be invited to participate in a survey interview to assess the usability of their assigned devices and record changes they have noticed. This survey will be developed after the study enrollment starts but before participants would need to complete the survey. A modification will be submitted to the Mayo Clinic IRB when the survey becomes ready. Subjects will be reimbursed for their time as described in the Budget Justification section. The participants may continue to use the MT nozzle, smart water bottle and its accompanying smartphone application after the study completion if they choose to without any additional study data collection. The participants in the placebo nozzle group will be provided with the MT nozzle for personal use upon request after the completion of the study. The human subject study will be approved by Institutional ReviewBoard (IRB) at Mayo Clinic Rochester. Statistical analysis methods are described in the Statistical Design and Power Section.

Metric of Success: Adherence is greater than 50% in the therapy group. There is statistically significant change in QOL of the therapy group compared to control group after 60 days of therapy.

Alternatives: If adherence is not greater than 50%, participants will be interviewed to understand what could be improved. If there are no statistically significant changes in QOL, sample size will be reviewed along with, AHI, SpO2, snoring measures, and the final survey interview to assess if there was notable improvement reported between the therapy and the control groups. More emphasis will be put on the analysis of the myofunctional assessment to look for trends to inform improvement of therapy and/or patient selection.

Timeline:

Specific Aims	Month					
	1-2 months	3-4 months	5-6 months	7-8 months	9-10 months	11-12 months
1) Characterize, Develop, and Test Pre-production MT Nozzles						
1.a) Build Nozzle with Consistent Radial Compression Force						
1.b) Control Nozzle Outlet Flow Resistance						
1.c) Perform Nozzle Durability Testing						
1.d) Develop Nozzle to Water Bottle Connection Interface						
2) Conduct Clinical Feasibility Study						
IRB Approval & Recruit Patients						
Conduct Clinical Feasibility Study						
Analyze Study Results						
Submit Final Report						

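### The waiver of the baseline WatchPAT ignores treatment status, so an on-treatment baseline can be compared with an off-treatment day-60 test

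*Protocol*

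**What the plan says.** The waiver is in the protocol's Approach, under Aim 2 (feasibility study in human subjects), where the baseline home sleep test is described. Its trigger is "If the subject has completed a WatchPAT clinically at Mayo Clinic within the last 3 months", and its effect is that "the baseline WatchPAT is not required to be sent to the participant as the clinical data is accessible and will still be valid". Place and recency are the only conditions.

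The same section sets a washout for "participants who are actively using CPAP, mandibular advancement device, or sleep positioning device": they "would be asked to discontinue the SOC treatment use for 3 nights prior to the baseline and end-of-study testing". The stated purpose is to clear residual effects of that treatment on the upper airway. The Inclusion Criteria add a matching requirement: "Willingness and ability to discontinue the currently prescribed OSA treatment for at least 3 days prior to testing".

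The WatchPAT measures are used as changes from baseline. Specific Aims, Aim 2 says: "Secondary outcome measures will compare changes in myofunctional assessment, AHI, oxygen saturation (SpO2), and snoring intensity/percentage". They also enter the fallback under Alternatives in the Aim 2 section: "If there are no statistically significant changes in QOL, sample size will be reviewed along with, AHI, SpO2, snoring measures".

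**The concern.** The washout rule shows that the protocol regards a test without 3 nights off treatment as unfit for measuring change. The waiver nevertheless declares an earlier clinical test valid without asking whether that condition was met.

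For a participant tested clinically on CPAP, a mandibular advancement device or a positional device, the baseline is on treatment. The day-60 test, under the washout rule, is off treatment. The change in pAHI, pRDI, ODI, nadir SpO2, T90 and snoring then contains two effects: the nozzle, and stopping SOC treatment. If treatment had lowered the baseline reading, the participant appears to worsen and a real benefit is hidden.

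Analysis cannot repair a baseline recorded under the wrong condition, least of all if treatment status was never captured. This is a data-collection rule and has to be right in the protocol.

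**Working it through.** **Does the text close the gap?** Three provisions bear on it.

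1. *Waiver (Aim 2).* Conditions: done at the site, within 3 months. Treatment status is not mentioned.
2. *Washout (Aim 2).* A request to participants to stop treatment before testing. Made at or after enrolment, it cannot alter a recording that already exists.
3. *Inclusion criterion.* Willingness and ability to stop before testing. This too looks forward and says nothing about a past test.

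Nothing else in the protocol limits the waiver to untreated or washed-out tests, or asks anyone to check. Treated patients are expected, since the washout names them. The qualifying diagnosis may be up to 2 years old, so a patient can be diagnosed, start treatment and have a later clinical WatchPAT inside the 3-month window.

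**Scale.** The protocol gives no figure to reproduce, so the following only illustrates the possible size.

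Inputs:
- n = 20 per arm, 40 in total (Aim 2).
- k = number of participants with an on/off mismatch: assumed 2, 4 or 8.
- d = amount by which treatment lowered the baseline reading: assumed 5 or 10 events/h, the same for all affected.

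Formulas:
- Effect of one mismatched participant on the arm's mean change: d/20, which is 5/20 = 0.25 or 10/20 = 0.5 events/h.
- Average within-arm shift: k·d/40.
- Number mismatched in one arm: X ~ Hypergeometric(40, k, 20), with variance k·(1/4)·(40 − k)/39.
- Shift in the arm difference: X·d/20 − (k − X)·d/20 = (2X − k)·d/20. Its mean is 0 and its SD is SD(X)·d/10.

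| k | SD(X) | Within-arm shift, d = 5 / 10 | SD of shift in arm difference, d = 5 / 10 | P(absolute shift ≥ 2 events/h), d = 5 / 10 |
|---|---|---|---|---|
| 2 | √(0.5·38/39) = 0.70 | 0.25 / 0.5 | 0.35 / 0.70 | 0 / 0 |
| 4 | √(1·36/39) = 0.96 | 0.5 / 1.0 | 0.48 / 0.96 | 0 / 10.6% |
| 8 | √(2·32/39) = 1.28 | 1.0 / 2.0 | 0.64 / 1.28 | 0.3% / 23.5% |

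The non-zero probabilities:
- k = 4, d = 10 needs X = 0 or 4: 2·C(20,4)/C(40,4) = 2·4,845/91,390 = 0.106.
- k = 8, d = 5 needs X = 0 or 8: 2·C(20,8)/C(40,8) = 2·125,970/76,904,685 = 0.003.
- k = 8, d = 10 needs X ≤ 2 or X ≥ 6: 2·(125,970 + 1,550,400 + 7,364,400)/76,904,685 = 0.235.

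With k = 0 every entry is zero.

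**The case against.** The other side has four points.

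*The washout rule can be read to cover any baseline, including a waived one.* It makes no exception for waiver users, and the waiver is permissive, so the team may still send a device. A careful team might read it that way. But the rule is worded as a request about future behaviour, and the waiver calls the earlier data valid outright. The text does not require the charitable reading.

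*The affected group is probably small.* A mismatch needs an active SOC user with a clinical WatchPAT at this site, within 3 months, recorded on treatment. The protocol describes home tests in this population as diagnostic, and a diagnostic test would ordinarily be untreated. A patient with a recent test may simply be newly diagnosed. This stands: the protocol makes a mismatch possible but does not show how often it would occur.

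*The magnitude is assumed.* This also stands. The 23.5% figure needs 8 of 40 participants mismatched by 10 events/h each. With 2 mismatched, a shift of 2 events/h cannot occur at either offset.

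*The consequences are limited.* The planned comparison is between arms. Whether someone has a qualifying clinical test is settled before randomization, so the expected shift in the arm difference is zero. The success metrics, adherence and QOL, do not use WatchPAT, nor does the myofunctional assessment, and efficacy is deferred to a later phase. All of this is right. It limits the importance of the point without removing it: the WatchPAT changes are named secondary outcomes, and the fallback reading of the trial draws on them if QOL is not significant.

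**Conclusion.** The concern holds. As written, the waiver can pair an on-treatment baseline with an off-treatment day-60 test, against the protocol's own washout rule, and nothing in the protocol prevents or detects it. The result is distorted within-arm change and extra noise in the arm difference for the WatchPAT secondary outcomes. Participants not on SOC treatment, or tested clinically off treatment, are unaffected.

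The size depends wholly on k and d, which the protocol does not give; the table above shows the assumed range. Confidence is medium, because how often a waived test would be on treatment is unknown. The change is still worth making: it is cheap now, and the error cannot be undone once data are collected.

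**What to change.** Add one sentence to the Aim 2 waiver: a clinical WatchPAT from the last 3 months may serve as baseline only if it was recorded with no SOC OSA treatment in use, or after at least 3 nights off it; otherwise the study baseline WatchPAT is done after the usual washout. Record three items for every baseline test: source (clinical or study), date, and treatment status.

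The cost is one sentence and three data fields. Some waiver users would need one additional home test after 3 nights off treatment, as other active SOC users already do. The participant kit described under Aim 2 already includes a WatchPAT ONE.
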